## PROTOCOL SYNOPSIS

**Protocol Title:** The Impact of Yttrium (Y90) Radiation Segmentectomy on Unresectable Hepatocellular Carcinoma

**Type of Protocol:** Phase I protocol to collect efficacy

**Protocol Design:** Prospective, open-label, single arm study.

**Study Objective:** The aim of this pilot study is to assess the efficacy of radiation segmentectomy with Theraspheres in patients with unresectable hepatocellular carcinoma that would qualify for thermal ablation as per the BCLC guidelines, but are unable to receive thermal ablation due to unfavorable location of target lesions.

**Primary Endpoint:** Efficacy of Yttrium (Y90) Radiation Segmentectomy on Unresectable Hepatocellular Carcinoma as measured by tumor response according to mRECIST based on investigator evaluations.

**Secondary Endpoints:**

- Time to Progression (TTP): The length of time from radiation segmentectomy until progression of disease based on mRECIST based on investigator evaluations.
- Assess toxicity resulting from Radiation Segmentectomy with Theraspheres

**Trial Population:** Patients diagnosed with Hepatocellular Carcinoma as per AASLD guidelines and not eligible for surgical resection or thermal ablation.

**Number of Patients:** 30

**Study Duration:** 2 years accrual and 2 years follow-up for a total of 4 years duration.

**Eligibility Criteria:**

1. Age greater than 18 years, regardless of race or gender
2. Hepatocellular Carcinoma confirmed by histology for non-cirrhotic patients or non-invasive criteria according to AASLD for cirrhotic patients.
3. Child-Pugh class A or B7 without ascites
4. Single tumor nodule  $\leq 3$  cm with a maximum distance of 5 mm from either portal vein, hepatic vein, inferior vena cava, diaphragm, heart, stomach, bowel, liver capsule, gallbladder, bile duct.
5. No prior locoregional treatment or external beam therapy of current HCC (recurrent HCC after resection may be included)
6. No confirmed extrahepatic metastases
7. No evidence of macrovascular invasion
8. ECOG 0
9. Albumin  $\geq 3.0$  g/dL

# The Impact of $^{90}\text{Yttrium}$ (Y90) Radiation Segmentectomy on Unresectable Hepatocellular Carcinoma

10. PLT  $\geq 40 \times 10^3/\mu\text{L}$
11. WBC  $\geq 1.5 \times 10^3/\mu\text{L}$
12. AST/ALT  $\leq 5$  times the upper limit of normal (U/L)
13. Creatinine  $\leq 2.0 \text{ mg/dL}$
14. No indication for any possible curative treatment after multidisciplinary assessment (surgery, ablation)
15. No contraindication to angiography or selective visceral catheterization
16. No history of severe allergy or intolerance to contrast agents, narcotics, sedatives.
17. Negative serum pregnancy test
18. Signed informed consent form

## Imaging Requirements

- MRI scans abdomen/pelvis; To assess disease extension and to determine liver volume measurement and identify hepatic vascular anatomy.
- Spiral CT Chest –performed with cuts of 10 mm or less in slice thickness contiguously in the axial plane. To assess extra-hepatic lesions according to the RECIST v 1.1.
- Hepatic angiography and 99mTC-MAA – selective celiac and superior mesenteric arteriograms are needed to evaluate the hepatic arterial anatomy for the whole liver, as well as evaluation of potential sources of extra-hepatic blood supply to tumors. Repeat 99mTC-MAA may be needed to estimate cumulative lung shunt or re-asses GI flow.
- SPECT imaging may be performed according to standard of care practices for clinical management but is not a study requirement.
- PET/CT for quantification of dose to target lesion, as well as dose to non-target liver.

## Sample Size Calculation and Statistical Plan

This is a pilot study seeking to determine the efficacy of radiation segmentectomy on very early to early unresectable HCC, not amenable to thermal ablation.

Current reported complete response rates of approximately 50% for BCLC A patients utilizing selective chemoembolization have been promising. (31,32,33) Radiofrequency ablation has been reported to have >80% complete response for lesions < 3 cm. (30)

Based on the assumption that a recent study reporting radiation segmentectomy rates similar to ablation, the goal is 80% complete response, compared to 50% complete response rate of TACE.

Numeric Results for testing  $H_0: P=P_0$  versus  $H_1: P \neq P_0$

Test Statistic: Z Test using S ( $P_0$ )

Proportion	Proportion
------------	------------

## The Impact of $^{90}\text{Yttrium (Y90)}$ Radiation Segmentectomy on Unresectable Hepatocellular Carcinoma

Power	N	Given H0		Given H1		Reject H0 If	
		(P0)		(P1)		Alpha	Beta If $[Z] >$ Then
0.9108	30	0.5000		0.8000		0.0500	0.0892 1.9600

A sample size of 30 achieves 91% power to detect a difference (P1-P0) of 0.3000 using a two-sided Z test that uses S(P0) to estimate the standard deviation. The target significance level is 0.0500. These results assume that the population proportion under the null hypothesis is 0.5000.

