# The Impact of Yttrium (Y90) Radiation Segmentectomy on Unresectable Hepatocellular Carcinoma

(4) perform technetium-99 m macroaggregated albumin (99mTc-MAA) scans to determine lung shunt fraction (LSF) and splanchnic shunting.

(5) Patients will not be eligible for TheraSphere infusion if the potential radiation dose to the lungs exceeds 30 Gy for a single treatment or cumulative 50 Gy or embolization cannot be performed to effectively block GI blood flow from the hepatic arterial system.

- In all patients, the vessel feeding the segment(s) being targeted for treatment will be identified and catheterized using standard angiographic techniques and conebeam CT.

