## c. *Delivery of Y90:*

- Radiation segmentectomy will be performed with Yttrium-90, whereby a high radiation dose is delivered to the tumor via radioactive microspheres infused through the hepatic artery. The radioactive microsphere delivery device used will be glass-based (TheraSphere; BTG, Ottawa, Ontario, Canada), in which 90Y is an integral constituent of the biocompatible glass matrix.
- Patients will be subsequently imaged the same day with PET-CT to calculate dose to target tissue, as well as dose to the non-target liver. This will be performed on a PET-CT system (Siemens).

Patients who consent to the procedure, but cannot proceed with treatment due to dose resulting in >30 Gy to the lungs or inability to target feeding vessels  $\leq$  2 Couinaud segments will be regarded as treatment failures.

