### c. Delivery of Y90:

- Radiation segmentectomy will be performed with Yttrium-90, whereby a high radiation dose is delivered to the tumor via radioactive microspheres infused through the hepatic artery. The radioactive microsphere delivery device used will be glass-based (TheraSphere; BTG, Ottawa, Ontario, Canada), in which Y is an integral constituent of the biocompatible glass matrix.
- Patients will be subsequently imaged the same day with PET-CT to quantify dose to target tissue, as well as dose to the non-target liver. This will be performed on a PET-CT system (Siemens).

Patients who consent to the procedure, but cannot proceed with treatment due to dose resulting in  $>30 \text{ Gy}$  to the lungs or inability to target feeding vessels  $\leq 2$  Couinaud segments will be regarded as treatment failures.

Termination of Participation in Study to include those subjects who did not pass Y90 mapping test, as well as those who have clinical deterioration of concurrent medical conditions and those who decide to terminate participation.

Patients will undergo routine clinical surveillance at 6 weeks post-Y90, 12 weeks post-Y90, and at 3 month intervals post-Y90 for 2 years post Y-90 during which time they will be evaluated by the physician assistant/nurse practitioner and attending physicians, with assessment of their clinical performance, active medical issues, and any toxicities, as graded by the NCI CTCAE version 4.03. Follow-up will be within 7 days of scheduled times post-treatment.

	Screening	Mapping	Y90 Treatment	6 wks post	12 wks post	6 mo post	9 mo	12 mo	15 mo	18 mo	24 mo	End of Study
Informed Consent	X											
Demographics	X											
Medical History	X											
Physical Exam	X											
ECOG	X	X	X	X	X	X	X	X	X	X	X	X
Child Pugh	X											
AFP	X	X		X	X	X	X	X	X	X	X	
Prior Treatment Hx	X											
Hematology	X	X		X	X	X	X	X	X	X	X	

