## The Impact of $^{90}\text{Yttrium}$ (Y90) Radiation Segmentectomy on Unresectable Hepatocellular Carcinoma

0.9108      30      0.5000      0.8000      0.0500    0.0892      1.9600

A sample size of 30 achieves 91% power to detect a difference ( $P_1 - P_0$ ) of 0.3000 using a two-sided Z test that uses  $S(P_0)$  to estimate the standard deviation. The target significance level is 0.0500. These results assume that the population proportion under the null hypothesis is 0.5000.

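### The tabulated power of 0.9108 (beta 0.0892) at N = 30 does not follow from the stated inputs; the exact power of the named test is 0.939

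*Combined protocol and SAP*

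**What the plan says.** The sample size justification appears twice with the same figures: in the Protocol Synopsis (Sample Size Calculation and Statistical Plan) and in Statistical Analysis (Sample size / Power Calculations). The rates are set by the statement that "the goal is 80% complete response, compared to 50% complete response rate of TACE". The test is a two-sided one-sample Z test of P = P0 with the standard deviation taken at P0.

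The single table row gives power 0.9108, N 30, P0 0.5000, P1 0.8000 and alpha 0.0500, then beta and the critical value as "0.0892 1.9600". The synopsis summarises this as "A sample size of 30 achieves 91% power to detect a difference (P1-P0) of 0.3000 using a two-sided Z test", and the Statistical Analysis section repeats it ("A sample size of 30 achieves 91% power to detect a difference").

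Neither place gives another N, a dropout allowance, a continuity correction, an attained significance level, or the method used to compute power.

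**The concern.** The row fixes everything needed to compute power, yet the printed power is not what those inputs give. This is not a misread table: 0.9108 and 0.0892 sum to 1, and both sections agree.

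It is the only quantitative support for N = 30, so a reader who checks it will find that it does not reproduce. The reader cannot then tell whether the output is wrong or one of the inputs, most obviously N, is not the one that was used.

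**Working it through.** **Inputs**, all from the table row and the text below it: N = 30, P0 = 0.50, P1 = 0.80, two-sided alpha 0.05, critical value 1.96, standard deviation S(P0).

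**Step 1. Rejection region.** Z = (x/30 − 0.5) / sqrt(0.25/30), and sqrt(0.25/30) = 0.0913.
- x = 20: Z = 0.1667/0.0913 = 1.826, not rejected.
- x = 21: Z = 0.2000/0.0913 = 2.191, rejected.
- By symmetry, x = 9 is rejected and x = 10 is not.

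The test rejects at 21 or more, or at 9 or fewer. Adding a continuity correction, or using the observed proportion for the standard deviation, leaves this region unchanged at N = 30.

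**Step 2. Exact size and power.**
- Size = 2 × P(X ≥ 21 | 30, 0.5) = 2 × 0.02139 = 0.0428.
- Power = P(X ≥ 21 | 30, 0.8) = 0.9389; the lower tail adds nothing visible. Beta = 1 − 0.9389 = 0.0611.
- Gap from the printed power: 0.9389 − 0.9108 = 0.0281, or 2.8 points.

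**Step 3. Attempts to reproduce 0.9108 at N = 30.**

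| Method | Power |
|---|---|
| Exact, reject at 20 or more | 0.9744 |
| Exact, reject at 21 or more (the named test) | 0.9389 |
| Exact, reject at 22 or more | 0.8713 |
| Normal, S(P0) under H0 and S(P1) under H1: Φ[(0.3 − 1.96 × 0.0913)/0.0730] | 0.9513 |
| As above with continuity correction: Φ[(0.3 − 1/60 − 1.96 × 0.0913)/0.0730] | 0.9236 |
| Arcsine | 0.9412 |
| S(P1) under both hypotheses: Φ(0.3/0.0730 − 1.96) | 0.9841 |
| S(P0) under both hypotheses: Φ(0.3/0.0913 − 1.96) | 0.9076 |

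Here 0.0730 = sqrt(0.16/30). No method returns 0.9108. The last row is the nearest and rounds to 91%.

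**Step 4. Other sample sizes.** For N from 22 to 35, the exact power of the named test equals 0.9108 to four decimals only at N = 24. There the test rejects at 17 or more (Z = 2.04 at 17/24, 1.63 at 16/24), exact power is 0.91083, beta is 0.0892 and exact two-sided size is 0.0639. N = 28 comes close, at 0.9100.

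**The case against.** The best defence is that nothing turns on the discrepancy. The plan does not say that power was computed exactly. The 91% in the prose is within rounding of 0.908, which uses S(P0) under both hypotheses. A difference of 2.8 points in a 30-patient pilot alters no decision. This largely stands: it limits the error to the four-decimal power and beta, and it keeps the point minor. It does not rescue the row, because 0.9076 is not 0.9108 and no other standard calculation at N = 30 gives the printed value.

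A reader might go further and infer from the match at N = 24 that the calculation was run for 24 evaluable patients and relabelled 30 after a 20% allowance (24/0.80 = 30), so that the test as planned exceeds its 0.05 level. The documents do not support this. They mention neither 24 nor a dropout allowance, and at the stated N of 30 the exact size is 0.043, below the target. The match is a reason to ask where the figure came from, not evidence of inflated type I error.

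**Conclusion.** The table row is wrong as written, and the error is minor. For the stated test at N = 30, exact power is 0.939 and beta 0.061, against 0.9108 and 0.0892 printed; exact size is 0.043.

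The statement that power is understated by 2.8 points rests on two conditions: all 30 patients are analysed, and the 80% rate applies to every patient counted. Under them N = 30 remains adequate and the rejection rule is unchanged.

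A reader might infer that the error is conservative in all circumstances. That goes too far. Exact power at N = 30 falls to 0.9108 when the true rate over all counted patients is 0.786 instead of 0.80, and the documents do not say whether the 80% includes patients who cannot be treated.

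Nor does the error show that the trial is underpowered or its denominator undefined. The plan gives no rate of failed mapping, and it already counts the main reasons for non-treatment as failures: "Patients who consent to the procedure, but cannot proceed with treatment due to dose resulting in >30 Gy to the lungs", or whose feeding vessels cannot be targeted within two "Couinaud segments will be regarded as treatment failures".

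**What to change.** Make the same correction in the Protocol Synopsis and in Statistical Analysis, in one of two ways:

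1. If 30 is the analysed number, replace the row and its sentence with: N = 30, exact power 0.94 (beta 0.06), H0 rejected in favour of a higher rate at 21 or more complete responses of 30, exact two-sided size 0.043.
2. If 0.9108 was computed for a different analysed number, state that number with its exact power and size. Were it 24, the entry would be power 0.911 and size 0.064, and the plan would then have to address a size above its 0.05 target.

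The cost is wording in two sections. Under the first option no patients are added, and N and the decision rule stay as they are.

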### Safety Analysis:

All patients will undergo safety analysis at the interval study visits outlined below in the study visits section. All adverse events will be reported according to the National Cancer Institute Common Terminology Criteria for Adverse Events v 4.03 (CTCAE). The incidence of adverse events will be summarized according to the primary system-organ class and within the category defined in the CTCAE v 4.03. The summaries will be overall (severity grades 1-4) and for grade  $\geq 3$  events and will also report the actions taken in terms of treatment discontinuation. Serious adverse events (SAE) will be tabulated by treatment. Laboratory values will be summarized by treatment group over time and overall.

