Slightly greater than half of the patients experienced adverse reactions and none required admission. The most common clinical toxicities according to the Common Terminology Criteria for Adverse Events v4 were fatigue (46), abdominal pain (10), nausea (8), fever (3), appetite loss (2), dyspnea (1), vomiting (1), and weight loss (1). The first four adverse events were all mild in nature. The most common grade 3/4 laboratory toxicities were lymphopenia, platelets, bilirubin, AST and ALT, hence many of these were present at baseline and not altered over a period of 24 months as demonstrated in Table 5 below.

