### **Secondary end points:**

1. Time to Progression: The length of time from radiation segmentectomy until progression of disease based on mRECIST.
2. Assess toxicity resulting from Radiation Segmentectomy with Theraspheres

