### **CAUSALITY (RELATIONSHIP TO MEDICAL DEVICE) ASSESSMENT**

The investigator or physician sub-investigator must indicate whether he/she believes the AE is not related, unlikely related, possibly related (reasonable possibility that the medical device caused the AE), probably related, or definitely related to the medical device. An adverse event becomes an adverse device effect when the adverse event is considered associated with the use of the test device if the attribution is Possibly, Probably or Definitely Related.

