### **PERIODIC SAFETY REPORTING**

Adverse events will be recorded on the AE form and coded using NCI CTCAE v 4.03. The investigator or physician sub-investigator will judge the severity of each AE and whether or not it is treatment-related. All AEs that occur after the initiation of trial treatment, including events likely to be related to the underlying disease or likely to represent concurrent illness, will be reported, including events present at Baseline which worsened during the trial.

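### The planned safety tables use neither the relationship rating nor a within-patient baseline comparison, so they cannot by themselves answer the endpoint of toxicity resulting from segmentectomy

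*Combined protocol and SAP*

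**What the plan says.** The endpoint is worded causally, both in the Synopsis and under Secondary end points: "Assess toxicity resulting from Radiation Segmentectomy with Theraspheres". The design is a "Prospective, open-label, single arm study".

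Safety Analysis in the Synopsis is the only place where safety tables are planned. For adverse events: "The incidence of adverse events will be summarized according to the primary system-organ class and within the category defined in the CTCAE v 4.03". These summaries are given overall and for grade 3 or higher, with actions taken in terms of treatment discontinuation. For serious events: "Serious adverse events (SAE) will be tabulated by treatment". For laboratory tests: "Laboratory values will be summarized by treatment group over time and overall". The later Statistical Analysis section says the study is to determine safety as well as efficacy, but contains only the response-rate power calculation.

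Other sections collect what an attributed analysis would need. Recording Adverse Events lists relationship to study treatment for each event. Under Causality Assessment the investigator "must indicate whether he/she believes the AE is not related" or related at one of four further levels. Events rated possibly, probably or definitely related are adverse device effects. Periodic Safety Reporting also requires events of other causes, "including events likely to be related to the underlying disease or likely to represent concurrent illness, will be reported", and counts conditions present at baseline if they worsened. The screening evaluations are designated as the baseline values.

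**The concern.** The endpoint asks what the procedure caused. The planned tables show what happened to patients after it, from any cause, over two years of follow-up. Without a control arm, no comparison group shows how many of those events would have occurred anyway.

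This population can be expected to have such events. The inclusion criteria allow Child-Pugh B7 without ascites and platelets down to 40 x 10^3/µL. They also list portal hypertension, platelets below 100 x 10^3/µL and bilirubin above 1.0 mg/dL among the reasons a patient counts as unresectable. The Background says of the grade 3/4 laboratory toxicities in a cited segmentectomy series that "many of these were present at baseline and not altered over a period of 24 months".

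The stake is interpretation of a named secondary endpoint. If the tables are produced as written, a reader cannot tell which events the investigator attributed to treatment, or which laboratory abnormalities are new. If attribution is added later, the rule (which rating levels count, which baseline is used) will be chosen after open-label data have been seen.

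**Working it through.** The plan states no figure on this point, so there is none to reproduce. The check compares what is collected with what is analysed, then gives an illustration of scale.

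**1. Collected against planned**

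| Item | Collected? | Used in Safety Analysis? |
|---|---|---|
| Organ class, CTCAE category, grade | Yes | Yes |
| Action taken | Yes (Recording Adverse Events) | Yes, as treatment discontinuation |
| Relationship, five levels | Yes (Recording Adverse Events; Causality Assessment) | No |
| Baseline laboratory values | Yes (Screening; Data Collection) | No within-patient comparison named; an over-time summary could display them |
| Treatment group | Not applicable, one arm | Named for SAEs and laboratory values |

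The relationship rating corresponds directly to the words of the endpoint, and no planned table uses it.

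**2. Illustration from Table 5 (Background)**

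Inputs are the counts at baseline (of 102) and at 1-3 months (of 94) in the cited retrospective series. Ratio = (baseline count/102) / (1-3 month count/94).

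| Test | Baseline | 1-3 months | Ratio |
|---|---|---|---|
| Lymphocytes | 16/102 = 15.7% | 18/94 = 19.1% | 0.82 |
| INR | 14/102 = 13.7% | 15/94 = 16.0% | 0.86 |
| Bilirubin | 3/102 = 2.9% | 6/94 = 6.4% | 0.46 |

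If those rates applied to the 30 planned patients:

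- Lymphocytes: 30 x 16/102 = 4.7 abnormal before treatment; 30 x 18/94 = 5.7 at 1-3 months.
- INR: 30 x 14/102 = 4.1 and 30 x 15/94 = 4.8.
- Bilirubin: 30 x 3/102 = 0.9 and 30 x 6/94 = 1.9.

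For lymphocytes and INR, a post-treatment count could therefore be largely background. For bilirubin it could be about half. By 3-6 months bilirubin is 7/53 = 13.2%, so baseline is 2.9/13.2, about 22%, of that rate. The share differs by test and by time.

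**3. Limits of the illustration**

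- The ratio compares two group rates with different denominators. It does not show whether the same patients were abnormal both times. A baseline-by-worst-grade table would show that.
- The text before Table 5 describes grade 3/4 toxicities, but the tests it names do not match the table's rows, so the grade is an assumption.
- The series was sicker: tumors up to 5 cm, 41 of 102 above ECOG 0, two patients Child-Pugh C. This trial requires ECOG 0 and limits bilirubin, albumin and AST/ALT at entry. Lymphocytes and INR have no limit of their own, although the white-cell and Child-Pugh criteria may restrict them indirectly.
- No comparable figure exists for the adverse event table.

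**The case against.** The strongest defence is that the attributed category already exists. Relationship is recorded for every event, the adverse device effect is defined, and the table could be produced at reporting without new data. All-cause reporting is also the cautious choice in an open-label pilot of 30 patients, where the investigator judges relatedness. This stands as a reason to keep the all-cause table. It does not supply an analysis for the endpoint, and it leaves the attribution rule to be settled after the data are known.

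Four stronger readings are tempting and are not supported:

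- A reader might infer that background liver disease will be reported as Y90 toxicity, or that toxicity will be overstated. No section says the all-cause table is the toxicity result. Baseline conditions count as adverse events only if they worsened, and a laboratory summary over time can show baseline beside follow-up, as Table 5 does.
- A reader might infer that relationship and baseline grade are the only ways to separate treatment effects from cirrhosis. Onset and resolution dates, expectedness and PET-CT dose to non-target liver are also recorded and can help.
- A reader might add the six rows of Table 5 into one ratio. That can count a patient several times, is dominated by lymphocytes and INR, and hides the much lower bilirubin ratio.
- A reader might call the treatment-discontinuation summary empty because each patient has one infusion. The schedule shows one treatment column, but the lung-dose limits refer to a single treatment and to a cumulative dose, so the documents do not settle this.

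**Conclusion.** The point holds as a mismatch between a stated endpoint and its stated analysis. The Safety Analysis paragraph cannot by itself answer the question of toxicity resulting from segmentectomy, because it uses neither the relationship rating nor a within-patient comparison with baseline grade. In a single-arm trial the tables may mix background disease with treatment effects. How far they would do so here is unknown. The ratios of 0.82, 0.86 and 0.46 rest on the assumption that a sicker series resembles this cohort, and they bear on laboratory results only.

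The change should be made before analysis. It does not affect the primary endpoint, the sample size or any formal test.

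**What to change.** In Safety Analysis:

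1. Define the toxicity endpoint as the number and percent of infused patients with at least one event rated possibly, probably or definitely related, for any grade and for grade 3 or higher. Show it beside the all-cause table.
2. Report laboratory toxicity as worst post-infusion CTCAE v4.03 grade cross-tabulated with baseline grade, test by test. State which pre-infusion result is the baseline: the screening evaluations are designated, but the schedule also has bloods at mapping.
3. As a minor clean-up, remove the references to tabulation by treatment and by treatment group.

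The cost is a few lines of text and two further tables, with no added patients or visits. One item needs confirming: the baseline list under Data Collection does not name a differential count, although the schedule has hematology at screening and mapping. A lymphocyte shift table needs that count. The downside is that relatedness is an investigator's judgement in an open-label trial and may under-attribute events, which is why the all-cause table stays.

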## **Serious Adverse Device Effect (SADE)**

A Serious Adverse Device Effect is an adverse device effect that has resulted in any of the consequences characteristic of a serious adverse event (SAE – previously defined) or might have led to any of these consequences if suitable action had not been taken; intervention had not been made or circumstances had been less fortunate. This is classified as Grade 3-4 as per the NCI CTCAE v4.03. If 5 Serious Adverse Events are recorded, the study will be discontinued.

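### The overall adverse event summary stops at grade 4 although its own grade 3-and-above subset does not, and the serious device effect definition conflicts with its grade label

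*Combined protocol and SAP*

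**What the plan says.** The only description of the safety analysis is under Safety Analysis in the protocol synopsis. It plans two adverse event summaries in one sentence: "The summaries will be overall (severity grades 1-4) and for grade" 3 and above, continuing "events and will also report the actions taken in terms of treatment discontinuation". The next sentence adds a third output: "Serious adverse events (SAE) will be tabulated by treatment". The later Statistical Analysis section covers sample size only and does not return to safety.

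Under Serious Adverse Device Effect (SADE), such an effect is first defined as one that "has resulted in any of the consequences characteristic of a serious adverse event", or might have done so in less fortunate circumstances. The section then says "This is classified as Grade 3-4 as per the NCI CTCAE v4.03", and immediately after that "If 5 Serious Adverse Events are recorded, the study will be discontinued".

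On collection, Periodic Safety Reporting covers "All AEs that occur after the initiation of trial treatment" and sets no grade limit. Recording Adverse Events requires seriousness and toxicity grade for each event.

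**The concern.** A table called overall should contain every event that appears in a table restricted to severe events. Here it does not. If the tables are programmed as written, a fatal event is counted in the severe table and left out of the any-grade one. A reader comparing the two could find a category in which severe events outnumber all events. Toxicity is a secondary endpoint, so this affects how a planned endpoint is reported.

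The device effect section has a related problem. Its first sentence classifies by consequence and its second by grade, and the two disagree about a fatal effect. The study's discontinuation sentence comes straight after, so a reader has to work out which class of event it counts.

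**Working it through.** No figure in the plan needs reproducing. The check sets the grade ranges side by side and then gauges how much they could matter. It assumes that grade 5 denotes death. That is standard CTCAE usage, but the documents do not say so.

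**Grade ranges as written**

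| Output or class | Section | Grades covered | Grade 5 included? |
|---|---|---|---|
| Overall summary | Safety Analysis | 1, 2, 3, 4 | No |
| Grade 3-and-above summary | Safety Analysis | 3, 4, 5 | Yes |
| Serious adverse event table | Safety Analysis | No limit stated | Not excluded |
| SADE, by consequence | SADE | No limit stated | Not excluded |
| SADE, by grade label | SADE | 3, 4 | No |
| Five-event discontinuation count | SADE | No limit stated | Not excluded |
| Adverse event collection | Periodic Safety Reporting | No limit stated | Not excluded |

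The set {3, 4, 5} is not contained in {1, 2, 3, 4}, so the first two rows are inconsistent. Rows four and five describe the same class and disagree. No other section corrects either mismatch, mentions grade 5 or plans a listing of deaths.

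**Effect on the overall table.** Take the planned 30 patients as the denominator. If k patients have a fatal event as their only event in a category, the any-grade incidence for that category is too low by k/30. For k = 1 this is 1/30 = 3.3 percentage points. In a category with that one event and no other, the overall table shows 0/30 and the grade 3-and-above table shows 1/30. A patient who also had a grade 1-4 event in the same category is still counted, so 3.3 points per patient is an upper limit.

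**Would a fatal event be likely?** The chance of at least one in 30 patients is 1 − (1 − p)^30, where p is the risk per patient:

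- p = 1% (assumed): 1 − 0.99^30 = 26%
- p = 3%: 1 − 0.97^30 = 60%, with 30 × 0.03 = 0.9 deaths expected
- p = 5% (assumed): 1 − 0.95^30 = 79%

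The 3% is the 30-day mortality that the Background quotes for a 291-patient TheraSphere cohort. The other two values only show the range. None is an estimate for this trial.

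**The case against.** The strongest reply is that little is lost. A death would appear in the grade 3-and-above summary and, as a serious event, in the serious adverse event table. All events after the start of treatment are collected, with their grade. A reader might infer from the 1-4 range that deaths would go unreported. The documents do not support that, and this part of the reply stands in full.

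A reader might also infer that fatal events are left out of the five-event discontinuation count, because the sentence follows the grade 3-4 label. The text does not say so. The label is attached to serious adverse device effects, whereas the count is of serious adverse events, a broader term with no grade limit. The section cites the underlying definition as "SAE – previously defined". That definition is not in the text available for this review, so nothing is built on it here. What remains is the conflict between the two sentences that describe a SADE, and the need to say plainly which events the next sentence counts.

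The 3% mortality is also a poor guide. That cohort averaged 1.8 treatments per patient and included Child-Pugh B patients with portal vein thrombosis. This trial requires ECOG 0, Child-Pugh A or B7 without ascites, one nodule of at most 3 cm and no macrovascular invasion. The 102-patient segmental series in the Background reports that no patient with adverse reactions was admitted, and the toxicity table of the 84-patient series lists no death. The 3% is also all-cause mortality, so it says nothing about device-related deaths. This stands, and the probabilities are therefore illustrative only.

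**Conclusion.** The point holds as a minor inconsistency in a stated analysis rule. Followed literally, the overall table leaves out events that its own severe subset contains. The any-grade incidence could be understated by up to 3.3 percentage points per affected patient, and the two tables would not agree. The SADE definition and its grade label also contradict each other on fatal effects. Both conclusions rest on reading the grade ranges as written and on grade 5 meaning death. Neither depends on any assumed death rate. The likely cause is a slip of wording, and no efficacy result or sample size is affected.

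**What to change.** Under Safety Analysis, replace the 1-4 range so that the overall summary covers all grades, 1 to 5, and add a sentence saying that deaths will be listed separately. The listing can use items already recorded for each event, such as onset and relationship to treatment.

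Under Serious Adverse Device Effect (SADE), the sponsor should reconcile the consequence-based definition with the grade label and state unambiguously which events the discontinuation sentence counts. The content of that rule is for the sponsor to decide.

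The cost is a few words in two sections. No extra data, visits or patients are needed.
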